6.2.2 Treatment period

The following has to be ensured during trial visits according to the study [Flow Chart](#):

- The PedsQL™ questionnaire must be always administered prior to any other procedures, and according to instructions given (see [Section 5.6.1](#) and [Appendix 10.7](#)).
- Blood draw for laboratory tests must be performed prior to administration of trial medication (applicable to Visit 2 and Visit 6 only; for the timing of blood draws to be conducted at Visit 3 and Visit 7 please refer to the [Flow Chart for PK blood sampling](#)).
- FVC measurements at all visits should be performed approximately at the same time of the day to reference time point at Visit 2.
- Order of pulmonary function tests at Visit 2 must be:
 1. FVC measurement with the spirometer provided, followed by patient's rest
 2. DLCO measurement with site's own equipment.

Visit 2 (baseline)

For the conduct of Visit 2 the following prerequisites must be met:

- Confirmation of fibrosing ILD based on HRCT central review (and biopsy central review if needed).
- Safety laboratory results from blood sampling conducted at Visit 1, including haemoglobin and creatinine measurements, have been provided and are available at the site.

If for any reason the screening phase for an individual patient lasts for more than 6 weeks, then the laboratory examination for Visit 1 has to be repeated before randomization. The screening phase (from informed consent until Visit 2) must be no longer than 12 weeks.

Observations and procedures:

- PedsQL™ questionnaire will be administered prior to any other procedures and checked for completeness (see [Section 5.6.1](#) and [Appendix 10.7](#)).
- Adverse events, any ILD exacerbations, respiratory-related hospitalizations [REDACTED], and concomitant therapy since last visit will be reviewed and recorded.
- Prior to blood draw, physical examination including vital signs, weight, height (standing and sitting), and leg length will be performed; data will be recorded in source documents and timely entered into the eCRF.
- If the ECG was abnormal at Visit 1, the 12-lead ECG at rest will be repeated (if possible prior to blood draw), and evaluated by qualified personnel at site.
- SpO₂ measurement will be conducted on room air at rest.
- FVC measurement will be conducted according to procedures defined (see ISF for details).

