- DLCO measurement will be conducted after FVC measurement and patient's rest. DLCO will be corrected for haemoglobin (Hb) measured at Visit 1 (see [Section 5.6.4](#) for details).
- The 6-minute walk test including Borg CR-10 scale[®] and continuous pulse oximetry (SpO₂) will be conducted per instructions given in [Section 5.1.6](#).
- All in/exclusion criteria will be checked, and if all in-/exclusion criteria are fulfilled the patient will qualify for the treatment period of the study.
- Blood and urine samples (safety laboratory tests, and pregnancy test on serum in female patients only) will be collected and submitted to the central laboratory.

- If a patient is eligible for the trial, randomization will be performed by using the IRT system.
- The assigned trial medication will be administered at the site. Medication wallets will be dispensed, patients and parent(s)/legal guardian will be properly instructed about how and when the study medication should be taken until the next visit. The parent(s)/legal guardian (and the patient, where applicable based on the patient's age) will be properly instructed to contact the site in case of adverse events (details given in the informed consent, and assent where applicable).
- A PK diary card will be dispensed; the patient and parent(s)/legal guardian will be instructed on how it should be completed in the 3 days before the next visit.
- The next visit will be scheduled; patient and parent(s)/legal guardian will be instructed on procedures to be followed until the next visit.
- An MRI of epiphyseal growth plates will be conducted* in all patients who qualified for randomisation according to protocol requirements (see [Section 5.2.5](#)). If MRI cannot be performed, an x-ray will be conducted. The MRI (or x-ray) will be sent to central evaluation by radiology expert on a timely manner.
- Dental examination will be conducted* in all patients who qualified for randomisation according to protocol requirements (see [Section 5.2.6](#)), and evaluated at site.
- Dental imaging will be conducted* in all patients who qualified for randomisation according to protocol requirements (see [Section 5.2.6](#)). The panoramic x-ray will be sent to central evaluation by a paediatric dentistry expert in a timely manner.

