*If it's not possible to conduct this procedure on the day of the visit, the procedure can be done in the 2 weeks immediately after the visit (please refer to the image acquisition guideline available in the ISF for details).

If by the end of Visit 2 the patient does not qualify for randomization, screening failure will be notified via IRT. Patient rescreening at a later date is possible. At due time a new informed consent (and assent where applicable) will be collected; site personnel will perform a re-screening call/notification in IRT to register patient's re-screening; the patient will be assigned a new patient number which will be linked to the original patient number, and

complete all study procedures according to [Flow Chart](#). Re-screening of a previously screen failed patient will be permitted once.

Results of laboratory examination of samples collected at Visit 2 will become available only after Visit 2. Since laboratory results from Visit 2 cannot be used to assess patient's eligibility, laboratory results from Visit 1 will be used instead. In case laboratory results of Visit 2 meet any exclusion criterion, the investigator must discuss the case with the sponsor, and obtain directions whether or not the patient should discontinue trial medication. The patient's conditions and the decision taken should be properly documented, reason for continuation should be justified in writing by the investigator.

Visit 3 and Visit 7 (visits with extensive PK)

For the conduct of Visit 3 and Visit 7 extensive PK the following prerequisites must be met:

- The patient has taken the trial medication in the three days preceding the visit as instructed.

If PK sampling needs to be repeated (see [Flow Chart for PK blood sampling](#) and [Section 5.3.1](#) for details), PK sampling will be repeated close before the end of treatment visit, to allow the maximum possible interval from the previous PK sampling.

Observations and procedures:

- The site personnel will check the PK diary card and confirm that the trial medication has been taken in the three days preceding the visit. If this is not confirmed, the visit will be rescheduled.
- Criteria for dose reduction / interruption will be checked, if any.

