- The site personnel will check the pregnancy test diary card (females only, and not to be done at Visit 4) and confirm that since the last scheduled visit at the site the pregnancy test has been repeated every 4-6 weeks until the current visit. If not confirmed, the investigator will re-instruct the patient and parent(s)/legal guardian. Test results will be documented in the patient's records. In case a positive test is reported the sponsor should be contacted immediately. Refer to [Section 3.3.4.1](#) for further instructions. Refer to [Section 5.2.7.2.3](#) for detailed information on event reporting in case of pregnancy.
- Adverse events, any ILD exacerbations, respiratory-related hospitalizations [REDACTED] and concomitant therapy since last visit will be reviewed and recorded.
- Prior to blood draw, physical examination including vital signs, weight, height, and leg length will be performed (height and leg length not planned at Visit 4; leg length planned every 24 weeks after the first year); data will be recorded in source documents and timely transferred per instructions provided (see ISF), to ensure central review as needed.
- The 12-lead ECG at rest will be conducted (if possible prior to blood draw), and evaluated by qualified personnel at site (Visit 6, Visit 9 and every 24 weeks after the first year only).
- SpO₂ measurement will be conducted on room air at rest.
- FVC measurement will be conducted according to procedures defined (see ISF for details).
- The 6-minute walk test including Borg CR-10 scale® and continuous pulse oximetry (SpO₂) will be conducted (Visit 6 and Visit 9 only).
- Blood and urine samples (safety laboratory tests, and pregnancy test on serum in female patients only) will be collected and submitted to the central laboratory.

- New medication wallets will be assigned by using the IRT system and dispensed, returned wallets will be collected as instructed (see ISF for details).
- Visit 6 only: The first dose of the open label trial medication will be administered at the site.
- Visit 6 only: The patient's acceptability questionnaire will be administered.

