| 
Pregnancy test on blood conducted at site using central lab kits – female subjects only
 | 
If blood sampling for pregnancy test at the trial site is not possible
 
 • Urine dipstick pregnancy tests will be used • Testing must occur every 4-6 weeks and results documented in the pregnancy test diary card. • The results of the pregnancy tests must be transferred to the investigator who ensures medical review, documents any test results as needed, and reports any positive results as defined by CTP. |

| STANDARD PROCEDURE | POSSIBLE MODIFICATION |
|--|---|
| | 
If pregnancy tests cannot be conducted every 4-6 weeks, the individual patient treatment needs to be interrupted upon discussion with the sponsor. Medical decision has to be documented in patient's source notes.
 |
| 
Follow-up monitoring of bone and teeth conducted at site/external facilities
 
 • Bone MRI/x-ray • Dental examination • Dental panoramic x-ray | 
If regular follow-up monitoring of bone and teeth at site is not possible
 
 • Bone MRI/x-ray, dental examination and dental panoramic x-ray can be performed at a local radiologist/ local dentist • The results (images and dental examination report) must be transferred to the investigator, who will send images to central reading, ensure medical review, and document any clinically relevant safety issue as an adverse event. 
Follow-up monitoring of bone and teeth should be conducted at the planned timepoint defined by CTP. If bone MRI/x-ray and/or dental examination cannot be conducted at least every 16 weeks (first year)/28 weeks (second year), and/or if dental panoramic x-ray cannot be conducted at least every 28 weeks (first year)/1 year (thereafter), the individual patient treatment needs to be interrupted upon discussion with the sponsor. Medical decision has to be documented in patient's source notes.
 |

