| Description of change | | In Flow Chart added to Visit 6 the procedure of IMP administration during the visit. In Flow Chart footnote 12 changed sentence to state that Part B will start once the first open label dose has been taken in the morning during the visit. In Section 6.1 specified that also the morning dose at Visit 2 and Visit 6 should be taken at the site. In section 6.2.2 specified that blood draw prior to administration of trial medication is applicable to Visit 2 and Visit 6 only, and that for the timing of blood draws to be conducted at Visit 3 and Visit 7 the Flow Chart for PK blood sampling should be referred to. Also specified that at Visit 6 the first dose of the open label trial medication will be administered at the site, then the patient's acceptability questionnaire will be administered. In preparation to Visit 6 the patient and parent(s)/legal guardian will be instructed that on the day of this visit the |

| | | |
|------------------------------|--|---|
| | | morning dose of trial medication should not be taken before going to the site, because the morning dose will be taken during the visit. |
| Rationale for change | | At Visit 6 the study medication should be taken at site to ensure monitoring of possible immediate adverse reactions in those patients who received placebo during Part A and will receive their first dose of active medication at Visit 6. |
| Section to be changed | | Flow Chart, Flow Chart footnote 9, Table 1.4.2:1, 5.2.3 Safety laboratory parameters, 6.2.2 Treatment period, 6.2.3 Follow-up period and trial completion |

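### At Visit 2, and by inference at Visit 6 for placebo patients, a girl can take her first nintedanib dose before that day's pregnancy result is known; a dipstick would narrow the gap cheaply

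*Protocol*

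**What the plan says.** **Visit 2 (Protocol 6.2.2).** The pregnancy test is part of the central laboratory sample: "Blood and urine samples (safety laboratory tests, and pregnancy test on serum in female patients only) will be collected and submitted to the central laboratory". Later at the same visit the patient is randomised, and "The assigned trial medication will be administered at the site". The protocol is open about the timing: "Since laboratory results from Visit 2 cannot be used to assess patient's eligibility, laboratory results from Visit 1 will be used instead". The note under exclusion criteria 1 to 3 (Section 3.3.3) also says that Visit 2 results follow randomisation. Pregnancy is exclusion criterion 16.

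**Visit 6 (Protocol 6.2.2).** The same central sample is listed, and "Visit 6 only: The first dose of the open label trial medication will be administered at the site". The Amendment 2 rationale (Section 11.2) says that on-site dosing was added for "those patients who received placebo during Part A and will receive their first dose of active medication at Visit 6".

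**Order of events.** The rule for both visits is "Blood draw for laboratory tests must be performed prior to administration of trial medication (applicable to Visit 2 and Visit 6 only"). It fixes when the blood is drawn, not when the result must be known.

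**Earlier results.** Before Visit 2 there is the Visit 1 serum test, which is repeated if screening exceeds 6 weeks. Before Visit 6 there are home tests every 4 to 6 weeks with dipsticks supplied from Visit 4, and the site reviews the diary (Flow Chart footnote 9; Section 6.2.2).

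**The concern.** The pregnancy test on the day of first dosing does not inform the decision to dose. At Visit 2 this follows directly from the text. At Visit 6 the same kind of sample is sent to the same laboratory and the dose is taken during the visit.

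A girl with an unrecognised pregnancy would take nintedanib that day if allocated to it at Visit 2, or at Visit 6 if she had been on placebo. She would go home with a supply, and the positive result would follow. Section 3.3.4.1 then requires treatment to stop at once, so exposure lasts for the laboratory turnaround, which is not given. Section 4.2.2.3 rates the drug's teratogenic and embryotoxic potential as high, and Table 1.4.2:1 lists foetal harm as a trial risk with pregnancy testing among its mitigations. At first exposure that mitigation rests on an old result.

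**Working it through.** The plan gives no figure of its own here. The check has two parts: the age of the last known result, and the chance that it matters.

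**1. Age of the last known result at first possible nintedanib dose**

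- Visit 2, on schedule: Visit 1 is at most 28 days before Visit 2 (Flow Chart), so the result is up to 28 days old.
- Visit 2, extended screening: the repeat is triggered only after 6 weeks (footnote 7), so the result is up to 6 × 7 = 42 days old. This assumes that consent was signed at Visit 1. It also assumes that the repeat covers β-HCG, which Table 5.2.3:1 lists among the safety tests. Beyond 6 weeks a repeat is required, but no maximum age is set for it.
- Visit 6, placebo arm: with compliant home testing every 4 to 6 weeks, the last result is up to 28 to 42 days old.

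**2. Chance of an undetected pregnancy at first dose**

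Inputs:
- r = 0.01 per year, the ceiling for a highly effective method (Section 3.3.2, criterion 3). No credit is given for the required barrier method or for abstinence.
- d = age of the last result in days, from part 1.
- n = number of females of childbearing potential. The documents do not give it. I assume 10 and show 5 and 20.
- Allocation 2:1, so 2/3 first meet nintedanib at Visit 2 and 1/3 at Visit 6.

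Per girl: p(d) = 1 − (1 − r)^(d/365.25).
- p(28) = 1 − 0.99^(28/365.25) = 0.0770%
- p(42) = 1 − 0.99^(42/365.25) = 0.1155%

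At least one among n girls: 1 − (1 − q)^n, where q is the per-girl risk in question.

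| Situation | q | n | Result |
|---|---|---|---|
| Visit 2, either arm, 28 days | 0.0770% | 10 | 0.77% |
| Visit 2, on nintedanib, 28 days | 2/3 × 0.0770% | 10 | 0.51% |
| Visit 6, placebo third, 28 days | 1/3 × 0.0770% | 10 | 0.26% |
| Visit 6, placebo third, 42 days | 1/3 × 0.1155% | 10 | 0.38% |
| First nintedanib dose at either visit (28 days at Visit 2, 42 at Visit 6) | 2/3 × 0.0770% + 1/3 × 0.1155% = 0.0898% | 10 | 0.89% |
| As above | 0.0898% | 5 | 0.45% |
| As above | 0.0898% | 20 | 1.78% |

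If every result were 42 days old at both visits, q = 0.1155% and n = 10 gives 1.15%. For Visit 2 alone, in either arm, the outer range runs from 0.38% (5 girls, 28 days) to 2.3% (20 girls, all at 42 days). The upper end stacks extreme assumptions in a trial that targets about 30 patients of both sexes aged 6 to 17.

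These figures count every conception since the last result. A dipstick would miss the most recent ones, so the preventable share is smaller.

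**The case against.** The strongest reply is that this is a deliberate, layered and disclosed policy. Contraception or abstinence is required, with contraception starting 28 days before treatment, which covers the on-schedule interval from Visit 1 to Visit 2. All criteria are checked on the day of Visit 2. Blood is tested at every visit until end of treatment, and urine between visits from Visit 4. On-treatment tests are themselves 4 to 6 weeks apart, so the plan already accepts a longer possible exposure than one laboratory turnaround. The investigator site file and country rules were not available. SAP Section 7.8.2.1 shows that country variants exist (a 4-week interval in Poland), and some sites may already test locally. An amendment also needs approvals across about 24 countries. All of this stands, and it lowers the probability and the priority. It does not put a current result in the investigator's hands before first exposure.

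A reader might draw three stronger conclusions, which the documents do not support.

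- **That no pregnancy test precedes the first dose.** The Visit 1 serum result, or the home test before Visit 6, is known beforehand. The issue is its age.
- **That late reporting at Visit 6 is stated.** It is stated only for Visit 2. For Visit 6 it is inferred from central testing and dosing during the visit. The Amendment 2 rationale for moving the Follow-up Visit test to urine, which was to have the result at once, gives indirect support.
- **That the last result at Visit 6 is routinely 84 days old (day 169 − day 85).** The diary check does say "If not confirmed, the investigator will re-instruct the patient and parent(s)/legal guardian", and the rule "If pregnancy tests cannot be conducted every 4-6 weeks, the individual patient treatment needs to be interrupted upon discussion with the sponsor" appears only in Appendix 10.9. But testing every 4 to 6 weeks is mandatory in Section 6.2.2, so 84 days requires a breach. Section 3.3.4.1 also provides for stopping treatment after repeated non-compliance with important procedures. The 84-day case carries no weight here.

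**Conclusion.** The point holds as a cheap patient-safety improvement. At Visit 2 the text is explicit: first dosing can precede the same-day pregnancy result, and eligibility rests on a result about 28 days old, or up to about 42 days before a repeat is triggered. At Visit 6 the same conclusion for placebo patients is a reasonable inference, with a last known result up to 4 to 6 weeks old under compliant home testing.

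The size is small: about 0.9% for the whole trial that at least one girl starts nintedanib with an undetected pregnancy. This rests on an assumed 10 girls of childbearing potential, failure at 1% per year, and results 28 days old at Visit 2 and 42 days old at Visit 6. The consequence would be serious. The plan does not contradict itself on this point, and no endpoint or analysis is affected.

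**What to change.** In Protocol Section 6.2.2 and Flow Chart footnote 9, require a documented negative urine dipstick for every female patient, on the urine already collected. Testing all females matches the protocol's existing rule. Where urine is not accepted, require a local blood test shortly before the visit, for example within about 3 days. The result should be in hand:

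- at Visit 2, before randomisation or first dose. This also covers patients who enter Part B directly, since they too pass through Visit 2 (Section 6.1);
- at Visit 6, before the first open-label dose.

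Keep the central serum test as confirmation.

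The cost is a few minutes per female patient at two visits, dipstick supply from Visit 2 instead of Visit 4, and an occasional extra local blood draw with possible scheduling delay. A protocol amendment is needed, which can be bundled with the next one. A dipstick can miss a very early pregnancy, so the contraception rule stays the main safeguard.

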6.2.3 Follow-up period and trial completion

Follow-up Visit

A Follow-up Visit should be conducted 28 days (+3 days) after the end of treatment in all patients who are not enrolled into the separate open label extension trial.

Observations and procedures:

- Adverse events, any ILD exacerbations, respiratory-related hospitalizations, and concomitant therapy since last visit will be reviewed and recorded.
- Physical examination including vital signs will be performed; weight and height will be repeated at follow-up in case of clinically relevant changes at EoT; data will be recorded in source documents and timely transferred per instructions provided (see ISF), to ensure central review as needed.
- Blood and urine samples will be repeated at follow-up in case of clinically relevant changes at EoT, unless the patient is enrolled into the open label extension trial.
- Pregnancy test on urines will be conducted in female patients only. Test results will be documented in the patient's records.
- Patient's participation will be concluded for patients with withdrawn consent (and/or assent as applicable) and do not attend future visits.

Trial completion

The trial completion CRF page must be filled-in when the patient has terminated the trial. The end of the trial for the individual patient is:

- For patients who have completed the study visits as scheduled and are enrolled into the separate open label extension trial, end of trial is at EoT.
- For patients who have completed the study visits as scheduled and are NOT enrolled into the separate open label extension trial, end of trial is at the follow-up visit.
- For patients who have NOT completed the study visits as scheduled and withdraw consent:
 - If consent withdrawal occurs at time of trial medication discontinuation, end of trial is at EoT visit followed by the follow-up visit.
 - If consent withdrawal occurs after EoT was already completed, then the patient should have a final visit based on their scheduled study visit.

After completion of the trial, patients who are enrolled into the open label extension trial will have access to treatment with nintedanib.

Patients who prematurely discontinued trial medication

In case a patient has permanently discontinued trial medication, for whatever reason, at the End of Treatment visit the patient will be encouraged to attend all future visits (except 'a-Visits') up to the end of trial as originally planned.

During these visits the patient will undergo the following observations and procedures:

- PedsQL™ questionnaire will be administered prior to any other procedures and checked for completeness (Visit 6 and Visit 9 only).
- Adverse events, any ILD exacerbations, respiratory-related hospitalizations [REDACTED] and concomitant therapy since last visit will be reviewed and recorded.
- Physical examination including vital signs, weight, height, and leg length will be performed (height and leg length not planned at Visit 4; leg length planned every 24 weeks after the first year); data will be recorded in source documents and timely transferred per instructions provided (see ISF), to ensure central review as needed.
- SpO₂ measurement will be conducted on room air at rest.
- FVC measurement will be conducted according to procedures defined (see ISF for details).
- The 6-minute walk test including Borg CR-10 scale® and continuous pulse oximetry (SpO₂) will be conducted (Visit 6 and Visit 9 only).

- The next visit will be scheduled; patient and parent(s)/legal guardian will be instructed on procedures to be followed until the next visit.
- Follow-up MRIs (or x-rays if baseline MRI was not possible) of epiphyseal growth plates will be conducted* - in patients with open physes only - at 12 weeks, 24 weeks, 36 weeks, 52 weeks and every 24 weeks thereafter, until the end of the study or closure of the physes. MRIs (or x-rays) will be sent to central evaluation by radiology expert on a timely manner.
- Follow-up dental examination will be conducted* in all patients at 12 weeks, 24 weeks, 36 weeks, 52 weeks and every 24 weeks thereafter until the end of the study.
- Follow-up dental imaging will be conducted* in all patients at 24 weeks, 52 weeks and every 48 weeks thereafter until the end of the study. Panoramic x-ray will be sent to central evaluation by paediatric dentistry expert on a timely manner.

*If it's not possible to conduct this procedure on the day of the visit, the procedure can be done in the week immediately before or after the visit (please refer to the image acquisition guideline available in the ISF for details).

These visits will be regarded as part of the trial despite the patient having discontinued trial medication.

The need for coming to future visits in case of prematurely discontinuation of trial medication will be explained to patients and parent(s)/legal guardian prior to start of trial participation.

[figure not shown]
Vital status information

In case of premature discontinuation of trial medication, if the patient does not attend future visits as planned, every attempt will be made to get information on vital status at 24 weeks after randomization, i.e. at the time of data cut-off for the primary analysis, at 52 weeks and at the end of the trial.

Permission to further contacts by site personnel, e.g. by telephone calls, to allow collection of the vital status must be given in the informed consent.

Collection of vital status will be performed in accordance with national ethical and regulatory guidelines.

If death occurs, the investigator will review the circumstances, including the relevant medical records, to ascertain the most likely primary and secondary causes of death. The cause of death will be adjudicated by the AC.

